8. ASSESSMENT OF EFFICACY

The first co-primary efficacy endpoint is to compare the changes to baseline of the cognitive scores as measured by ADAS-Cog between each of the three treatment arms and the control group and between the three treatment arms themselves. The second of the co-primary efficacy endpoints is to compare the changes to baseline of the ADCS-ADL inventory scores between each of the three treatment arms and the control group and between the three treatment arms themselves.

The secondary efficacy endpoint is to assess the variations in other cognitive scores, AD biomarkers and other biochemical parameters.

8.1 Efficacy variables

Change from baseline in the cognitive scores as measured by ADAS-Cog (6 measurements: weeks -3, -2 or -1, and 7-8, months 6, 9, 12 and 14).

Change from baseline in the ADCS-ADL inventory (6 measurements: weeks -3, -2 or -1 and 7-8; month 6, 9, 12 and 14).

8.2 Secondary efficacy variables

- Change from baseline in the cognitive, functional and neuropsychiatric scores and overall development as measured by MMSE, NPS battery, NPI, CDR-Sb, ADCS-CGIC, CSDD, C-SSRS. (6 measurements: weeks -3, -2 or -1 and 7-8, month 6, 9, 12 and 14) and QoL-AD, RUD-Lite[®] (5 measurements: weeks -3, -2 or -1; months 6, 9, 12 and 14). Moreover the optional questionnaires like OAS and ABS could be used at any visit in case any sign of aggression or restlessness.
- Variation in levels of $A\beta_{1-40}$ and $A\beta_{1-42}$ in CSF in the period between baseline lumbar puncture (before the start of the intensive treatment period) and lumbar puncture immediately after the end of the last plasma exchange (whenever this may be).
- Variation in the levels of $A\beta_{1-40}$ and $A\beta_{1-42}$ in CSF between the finalization and beginning of each of the 2 treatment periods.
- Levels of $A\beta_{1-40}$, $A\beta_{1-42}$, T-tau and P-tau in CSF throughout the study.
- Plasma levels of $A\beta_{1-40}$ and $A\beta_{1-42}$ before and after each plasma exchange for both treatment periods.
- Structural changes in volume of the hippocampus, posterior cingulate area, and other associated areas by MRI. Five measurements will be made (weeks -3, -2 or -1 and 7-8; months 6, 9 and 14).
- Variation in FDG-PET patterns (4 measurements: weeks -3, -2 or -1 and 7-8; months 9, and 14).

8.3 Safety variables

The primary criterion of safety will be the percentage of plasma exchanges (full and low-volume exchanges, including the infusion of albumin and IVIG) associated with at least one adverse event that may be related to the study procedure (adverse reactions) within 72 hours after infusion completion (or after the infusion stops). In addition, consideration globally will be made of the percentage plasma exchanges (full and low-volume exchanges, including the infusion of albumin and IVIG) involving some adverse event, whether or not related to the procedure.

Vital signs (blood pressure, heart rate, respiration rate and body temperature) will be recorded before, during and after each plasma exchange session, where required. Evaluation will also be made (where required) of the different laboratory test parameters (blood cell counts, platelet count, troponin, prothrombin time (Quick), aPPT, fibrinogen, total proteins, and calcium).

During the treatment periods (before each plasma exchange) and on the days when there is no replacement, anxiety and restlessness tests will be made based on the Overt Aggression Scale (OAS) and the Agitated Behavior Scale (ABS), whenever considered opportune.

According to the criterion of the investigator, all the clinically important changes in vital function, laboratory test parameters and neuroimaging findings will be evaluated.

9. ASSESSMENT OF SAFETY

9.1 Adverse Events

9.1.1 Information to specify

Descriptions/Definitions:

- *Adverse Event (AE)* is any untoward medical occurrence in a patient or clinical trial subject administered a medicinal product and which does not necessarily have a causal relationship with this treatment.

- *Adverse Reaction (AR)* is all untoward and unintended responses to an investigational medicinal product related to any does administered.

- *Serious Adverse Event (SAE) or Serious Adverse Reaction (SAR)* is any untoward medical occurrence or effect that at any dose results in death, is life-threatening, requires hospitalization or prolongation of existing hospitalization, results in persistent or significant disability or incapacity, or is a congenital anomaly or birth defect.

Likewise, medical criterion will decide whether an event is serious in other situations such as those requiring intervention to prevent some of the aforementioned consequences.

Medical and scientific criteria will decide whether other situations that have not led to the outcomes listed in the above definitions should be notified as SAE.

By life-threatening event, it is understood a situation which according to the investigator opinion, would have led to the patient death in the absence of a timely therapeutic intervention.

- *Unexpected Adverse Event:* any adverse experience of a nature or severity that does not correspond to the information available in reference to the investigational procedure or study drug. Once the adverse event has been evaluated and reasonable bases are established for suspecting a causal relation to the study procedure and the SPC for the study drugs, the event is to be classified as an **adverse reaction** to the procedure or to the drug.

Detection and recording:

- *Method of Detection:* The AEs will be daily collected from a careful clinical observation of the patient, laboratory analyses, spontaneous communication from the patient and also through and open questioning from the investigator

- *Adverse events recording:* All adverse events and serious adverse events will be recorded in the patient's medical records and in the CRF (Adverse Events Form). In addition, the adverse

events related to the Auto-C (FDA PMA approval # BP850001) or Aurora (FDA 510(k) clearance # BK110072) based devices used in the low-volume plasma exchanges (Maintenance period) will be recorded in the specific form attached to the Auto-C (FDA PMA approval # BP850001) or Aurora (FDA 510(k) clearance # BK110072) clinical protocols (**Appendix 3**).

In the context of this clinical trial, all incidents clearly related to progression of the disease will not be considered as adverse events, and will not be necessary to include them in the CRF.

All adverse events occurring during the study are should be included in the CRF of the corresponding patient. The minimum information to be supplied comprises the nature of the event, its time of appearance in relation to the administration, its duration, dose, seriousness, intensity, causality, the actions taken, and the course. If it is a preexisting AE that gets worse regarding intensity or frequency it should be indicated.

Adverse events will be classified according to severity, depending on the intensity of the event, as follows:

Mild, when well tolerated by the patient, causing only minimal discomfort, and without interfering with the activities of daily living (ADL)

Moderate, when interfering with activities of daily living

Intense or severe, when impeding activities of daily living

Severity must be distinguished from seriousness, which is based on the consequence of the adverse event. For example, a headache may be mild, moderate or severe, though rarely is it serious.

9.1.2 Imputability criteria

To analyze the possible relation cause-effect, it will be considered the temporal relationship between drug administration and the AE, possible alternative causes, evolution (complete remission, partial recovery, death and sequelae), persistence or not after drug discontinuation, reappearance with drug re-administration, or the previous knowledge of the event matching up with the known or expected response pattern of the study drug.

The following definitions will be used to establish cause-effect relationships:

Definitive: the adverse event occurs after a reasonable time sequence related to the study drug administration or study procedure, with a known response model, but cannot be explained by the patient clinical condition and other treatments provided, confirmed by improvement after interrupting or diminishing treatment dose, and with relapse after reintroducing treatment.

Probable: the adverse event occurs after a reasonable time sequence related to the study drug administration or study procedure, with a known response model, confirmed by improvement after interrupting treatment, and that cannot be explained by the patient clinical condition or other treatments provided.

Possible: the adverse event occurs after a reasonable time sequence related to the study drug administration or study procedure, with a known response model, but can be explained by the patient clinical condition and other treatments provided.

Unlikely: the adverse event occurs after a reasonable time sequence related to the study drug administration or study procedure, not following a known response model, and that cannot be explained by the patient clinical condition or other treatments provided.

Unrelated: Any other adverse event.

9.1.3 *Expected adverse events*

There are a series of **expected adverse events** attributable to the plasma exchange procedure, with others that are inherent to the replacement fluid used (human albumin). Lastly, other events are a consequence of patient disease or idiosyncrasy.

The expected adverse events of plasma exchange are the following: hypocalcaemia (manifesting as paresthesias, headache, vision alterations, nausea, cramps and chest oppression), anaemia and coagulation disorders secondary to coagulation factor dilution (mainly hypofibrinogenemia, with possible minor bleeding associated to severe thrombopenia). Hypotension may occur (accompanied by paleness, perspiration, bradycardia, nausea, vomiting, syncope, sphincter relaxation and seizures); though the risk is minimal, since the infusion amount is equivalent to the extracted amount. Allergic reactions are also possible, with urticaria, dyspnea, wheezing, hypotension, tachycardia, facial reddening and palpebral edema. Other events may be of psychological origin or may be inherent to the process, such as for example pain after remaining immobile for several hours.

As indicated by the **Full Prescribing Information (Appendix 1)**, the Albutein[®] specific adverse events are mild reactions such as reddening, urticaria, fever and nausea. Such reactions are rare and normally subside when the perfusion rate is reduced or perfusion is suspended. Anaphylactic shock may be observed in isolated cases. In such situations, perfusion is to be suspended immediately with the provision of adequate treatment.

Albutein[®] is obtained from human plasma. The controls applied in the centers where the plasma is obtained, and in the fractionation plant, as well as the validated infectious agent inactivation/elimination procedures included in the production process, are all designed to minimize the risk of transmission of infectious disease. In any case, when dealing with blood products it is not possible to fully rule out possible transmission of infectious agents. This also refers to the possible transmission of unknown pathogens.

In a 1996 review of the adverse effects of plasma exchange in patients with Guillain-Barré syndrome involving albumin replacements, a decrease in immediate adverse effects from 12% in 1986 to 7% in 1992 was recorded. Allergic reactions and hypotension were the most frequent problems. The estimated mortality was 1-2 deaths per 10,000 sessions, or two deaths per 2000 patients.

With regard to Flebogamma[®]DIF (see **Full Prescribing Information, Appendix 2**) Adverse reactions such as chills, headache, fever, vomiting, allergic reactions, nausea, arthralgia, low blood pressure and moderate low back pain may occur occasionally. Rarely human normal immunoglobulins may cause a sudden fall in blood pressure and, in isolated cases, anaphylactic shock, even when the patient has shown no hypersensitivity to previous administration. Cases of reversible aseptic meningitis, isolated cases of reversible haemolytic anaemia/haemolysis and rare cases of transient cutaneous reactions, have been observed with human normal immunoglobulin. Increase in serum creatinine level and/or acute renal failure have been observed. Very rarely: Thromboembolic reactions such as myocardial infarction, stroke, pulmonary embolism, deep vein thromboses.

In addition, there may be adverse events related to the concomitant medication provided. Thus, acetylcholinesterase inhibitors have been associated with diarrhea, muscle cramps, fatigue, nausea, vomiting, insomnia, headache, pain, accidents, common cold, gastrointestinal problems and dizziness. There have also been sporadic reports of syncope, bradycardia, sinoatrial block, atrioventricular block, seizures, liver dysfunction, psychiatric problems

(hallucinations, restlessness and aggressive behavior), anorexia, gastric and duodenal ulcers, gastrointestinal bleeding, extrapyramidal symptoms, and a small increase in serum muscle creatine kinase (CK).

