10.4 Intermediate Analysis and Stopping Rules

A descriptive analysis is planned once half of the subjects are undergoing low-volume plasma exchanges.

Serious adverse events related to full plasma exchanges (performed during the first six weeks), AEs leading to withdrawal of the study and additional safety measures if required will be monitored by the independent DMC on a regular basis. Special focus will be put on those SAEs considered as related to the therapeutic procedure or Investigational Product(s) by the Principal Investigator as defined in the protocol. Additional common side effects might also be analyzed if significantly higher proportions are found in any of the treatment arms.

Under the following circumstances the independent DMC will recommend to halt the trial partly (stopping a specific treatment arm) temporarily (until modifications to the protocol are completed) or wholly (abandon all study activities):

- If more than 30% of patients undergoing full plasma exchanges experience an SAE as defined by the protocol labeled “Definitively related to the therapeutic procedure” or “Probably related to the therapeutic procedure” or “Possibly related to the therapeutic procedure” and not attributable to the Investigational Products, as judged by the principal investigator.

- If more than 30% of patients undergoing full plasma exchanges experience an SAE as defined by the protocol labeled “Definitively related to the Investigational Product(s)” or “Probably related to the Investigational Product(s)” or “Possibly related to the Investigational Product(s)” and not attributable to the therapeutic procedure or technique of application, as judged by the principal investigator.

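### The causality definitions in Protocol 9.1.2 label an unexplained, known-pattern event that does not improve as Unrelated, which takes it out of the relatedness-based safety outputs

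*Protocol*

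**What the plan says.** Protocol 9.1.2 lists factors to weigh, with death and sequelae among the outcomes, and then states that five definitions will be used to assign causality to the study drug or procedure. The first four all presuppose plausible timing.

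- **Definitive**: known pattern, no alternative explanation, and "confirmed by improvement after interrupting or diminishing treatment dose, and with relapse after reintroducing treatment".
- **Probable**: known pattern, and "confirmed by improvement after interrupting treatment, and that cannot be explained by the patient clinical condition or other treatments provided".
- **Possible**: "with a known response model, but can be explained by the patient clinical condition and other treatments provided".
- **Unlikely**: "not following a known response model, and that cannot be explained by the patient clinical condition or other treatments provided".
- **Unrelated**: a remainder, "Any other adverse event".

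The labels are used in several places. SAP 7.2.2 counts Unrelated as Not Related, and counts Possibly, Probably, Unlikely or missing as Related; Definitive is not on that list. SAP 7.2.1 builds the primary safety criterion on exchanges followed within 72 hours by an event that may be related to the procedure. Protocol 10.4 sets two DMC criteria, each beginning "If more than 30% of patients undergoing full plasma exchanges experience an SAE as defined by the protocol labeled", and both count only the definitive, probable and possible labels as judged by the principal investigator.

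The protocol itself expects harms that can be fatal or permanent. For the immunoglobulin, 9.1.3 lists "Very rarely: Thromboembolic reactions such as myocardial infarction, stroke, pulmonary embolism, deep vein thromboses" as well as acute renal failure. The same section cites a mortality for plasma exchange, and Appendix 12 covers catheter-related pulmonary embolism during the full-exchange period.

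**The concern.** A causality scale should move an event towards related when the timing fits, the pattern is familiar and nothing else explains it. Here the strongest circumstantial case drops to the bottom of the scale if the patient dies or does not recover, because improvement is built into both upper categories and no other category is open to an unexplained event with a known pattern. Adding a competing explanation raises the same event to Possible.

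What is at stake is attribution. With rare serious events, the label on each one carries most of the relatedness conclusion. One unexplained procedure death recorded as Unrelated would appear as Not Related in the SAP's tables, whereas the same death with the causality field left blank would be counted as Related there.

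**Working it through.** **Classification.** The documents give no figure to reproduce, so the check applies the printed definitions to every case. Take plausible timing as given and use four yes/no facts: known pattern, alternative explanation, improvement on interruption, and relapse on re-exposure. Relapse without prior improvement is excluded, which leaves 12 combinations.

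| Known pattern | Alternative explanation | Improves | Relapses | Combinations | Category | SAP 7.2.2 | Counted in 10.4 |
|---|---|---|---|---|---|---|---|
| yes | no | yes | yes | 1 | Definitive | not assigned | yes |
| yes | no | yes | no | 1 | Probable | Related | yes |
| yes | no | no | no | 1 | **Unrelated** | **Not Related** | **no** |
| yes | yes | any | any | 3 | Possible | Related | yes |
| no | no | any | any | 3 | Unlikely | Related | no |
| no | yes | any | any | 3 | Unrelated | Not Related | no |

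The third row is the gap: it is the only known-pattern combination that ends in Unrelated. A fatal event must fall there if nothing else explains it, because it cannot improve. An event that starts after a completed weekly or monthly session may fall there too, since there is no longer a treatment in progress to interrupt.

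The fifth row is a separate and smaller matter. Unexplained events of unknown pattern are Unlikely. The SAP counts them as Related, and the SAE completion guidelines in Appendix 4 treat Unlikely as potentially related to study drug. Only the 10.4 criteria leave them out.

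**Scale, on planned numbers.**

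- Active patients: 364 × 3/4 = 273 (Protocol 3.2 and 4.3).
- Full exchanges, if all six are given: 273 × 6 = 1,638.
- Expected deaths at the cited 1 to 2 per 10,000 sessions (9.1.3): 1,638 × 1/10,000 = 0.16 to 1,638 × 2/10,000 = 0.33.
- By the same source's per-patient figure of 2 in 2,000: 273 × 2/2,000 = 0.27.
- DMC threshold: more than 0.30 × 273 = 81.9, so 82 patients. If only the 312 evaluable subjects are counted, 312 × 3/4 = 234 active and 0.30 × 234 = 70.2, so 71 patients.

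**The case against.** The strongest reply is that a reader might infer that the worst expected harms vanish from the trial's safety record. The documents do not support that. SAP 7.2.2 tabulates all AEs, all SAEs and fatal SAEs whatever their causality, and lists deaths. Protocol 9.2 sends every SAE to the safety team within 24 hours regardless of causality. Under 12.4 the DMC compares unblinded event rates by arm, with special attention to serious events.

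Four other stronger readings also fail.

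- *The DMC halting rule is disabled.* It needs 82 patients, and the expected number of affected events is a fraction of one death plus some irreversible non-fatal events. This gap would not decide a halt.
- *Expected deaths are 0.5 to 1.0.* That comes from applying the mortality figure to all 18 sessions (273 × 18 = 4,914, giving 0.49 to 0.98). Protocol 5.2.2.7 expects a much lower event rate in the low-volume sessions, so full exchanges alone are the fair base.
- *New kinds of reaction are lost.* They are labelled Unlikely, which the SAP counts as Related.
- *Prompt regulatory reporting fails.* The rule in 9.2 covers serious, unexpected, potentially related events. Gap events have a known pattern and are mostly expected. The exception is a severity beyond what is known, because 9.1.1 defines unexpected by nature or severity.

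It is also fair that many thromboembolic or renal events in patients aged 55 to 85 will have a plausible alternative explanation and so be Possible, and that an investigator may override the definitions on judgement. The first narrows the affected group. The second does not close the gap: the protocol says the definitions will be used, gives no branch for death or sequelae, and the SAE form repeats the labels without defining them. Relying on departures from the text would make attribution vary by site.

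**Conclusion.** The concern holds in a limited form. On the printed text, a known-pattern, unexplained event that does not improve can only be Unrelated. It then leaves the SAP Related AE and SAE tables, the primary safety criterion and the numerators of both DMC 30% criteria, while remaining in the outputs that ignore causality. Unexplained events of unknown pattern are missed by the 10.4 criteria only.

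The number of events is likely to be small: about 0.16 to 0.33 expected procedure deaths over 1,638 full exchanges, not all of them without another explanation. The consequence is misstated relatedness, not a changed halting decision.

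This rests on investigators applying the definitions as written, on planned enrolment with all six full exchanges given, and on a mortality figure from patients with Guillain-Barré syndrome carrying over to this population. The classification result depends on the first of these only.

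**What to change.** **Protocol 9.1.2.**

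- Require improvement on interruption for Probable only where it can be assessed, and not where the event is fatal, irreversible or followed a completed session.
- Class plausible timing with no alternative explanation as at least Possible, whether or not the pattern is known.
- Define Unrelated by its own criteria instead of as the remainder.

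**SAP 7.2.2.** Align the Related/Not Related mapping with the revised categories and assign Definitive, which the Related list omits. The two documents must change together: unexplained events would move up to Possible, so Unlikely would need a new meaning. If it came to mean a more likely alternative cause while the SAP still counted it as Related, the Related tables would fill with events judged to have another cause. The Appendix 4 guidance on Unlikely needs the same alignment.

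**Before database lock.** Have the causality of all SAEs re-checked against the corrected text, in both directions and without reference to treatment arm where possible. Protocol 3.4 states blinding for patients, caregivers and raters only, and the SAE form records the arm. Revisiting only events labelled Unlikely or Unrelated could therefore shift labels one way with knowledge of treatment.

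**Cost.** Wording changes in the protocol and SAP, a site memo and one query round. A few more events will be labelled related. No treatment, visit or efficacy analysis changes.
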